6.2 Preparation/Handling/Storage/Accountability

6.2.1 Packaging and Labeling

All IP used in this study will be commercial products. Each carton will bear a label conforming to regulatory guidelines, Good Manufacturing Practice (GMP) and local laws and regulations that identifies the contents as investigational drug.

Refer to the product label and package insert [Betmiga Package Insert, Aug 2019] for detailed information regarding packaging and labeling of the IP.

6.2.2 Handling, Storage and Accountability

1. The investigator or designee must confirm appropriate temperature conditions have been maintained during transit for all IP received and any discrepancies are reported and resolved before use of the IP.
2. Only subjects enrolled in the study may receive IP and only authorized study site personnel may supply or administer IP. Only IP with appropriate expiry/retest dating may be dispensed.
3. All IP must be stored in a secure, environmentally controlled and monitored (manual or automated) area in accordance with the labeled storage conditions and access must be limited to the investigator and authorized study site personnel.
4. The investigator, institution or the head of the medical institution (where applicable) is responsible for accountability, reconciliation and record maintenance (i.e., receipt, reconciliation and final disposition records).

Refer to the package insert [Betmiga Package Insert, Aug 2019] for detailed information regarding handling and storage of the IP.

6.3 Randomization and Blinding

6.3.1 Blinding Method

Not applicable.

6.3.2 Assignment and Allocation

6.3.2.1 Subject Number

Subjects will be assigned a subject number at study entry (i.e., signing the ICF). The subject numbers will be sequential and rising.

The subject number will comprise of a 5-digit clinical unit number and 5-digit screening number.

6.3.2.2 Randomization Number

Subjects will be randomized in a 1:1:1:1 ratio to a dosing sequence according to the randomization schedule. All subjects who meet the eligibility criteria will be randomized.

Prior to dosing on day 1 of period 1, subjects will be assigned a randomization number in accordance with the randomization code generated by the sponsor's designee.

Once a randomization number has been allocated to a subject, it will not be assigned to another subject. If a subject withdraws prematurely from the study and is replaced under the direction of the sponsor, then a replacement randomization number will be assigned. A replacement randomization code will be generated such that replacement subjects are assigned to the same dosing sequence as the discontinued subject.

6.4 Investigational Product(s) Compliance

Dosing will take place in the clinical unit. The administration of IP will be supervised to ensure study compliance. After IP administration, a check of the subject's mouth and hands will be performed. The exact day and time of IP administration will be documented.

6.5 Previous and Concomitant Treatment (Medication and Nonmedication Therapy)

6.5.1 Previous Treatment (Medication and Nonmedication Therapy)

All medicinal products, including prescribed or nonprescribed drugs, used prior to first IP administration will be considered previous medication.

The subjects must abstain from use of any prescribed or nonprescribed drugs (including vitamins, natural and herbal remedies, e.g., St. John's Wort and traditional Chinese medicine) in the 2 weeks prior to first IP administration, except for:

- Paracetamol (up to 2 g/day)
- Topical dermatological products, including corticosteroid products
- Hormonal contraceptives
- HRT

At the screening, subjects will be questioned regarding the medicinal products that they have been taking over the past 3 months. All medication taken within 4 weeks prior to first admission to the clinical unit will be documented.

6.5.2 Concomitant Treatment (Medication and Nonmedication Therapy)

All medicinal products other than the IP(s), including prescribed or nonprescribed drugs (including vitamins, natural and herbal remedies, e.g., St. John's Wort and traditional Chinese medicine), used from first IP administration until the ESV (including washout between periods) will be considered concomitant medication.

Subjects will only be allowed to use the following concomitant medication, if needed, from first IP administration until the ESV (including washout between periods):

- Paracetamol (up to 2 g/day)
- Topical dermatological products, including corticosteroid products
- Hormonal contraceptives
- HRT

If a subject's health condition necessitates the use of any medication other than the permitted medications during the study, the investigator and medical monitor, or designee(s), will discuss the case and determine if the subject should be withdrawn from the study and/or excluded from analysis sets, depending on if, and how, the medication(s) used influence(s) the study outcome. The nonpermitted concomitant medication will be recorded as a protocol deviation (see [Section 9.9 Major Protocol Deviations]).

All concomitant treatment (medication and nonmedication therapy) will be documented within the source.

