All medicinal products other than the IP(s), including prescribed or nonprescribed drugs (including vitamins, natural and herbal remedies, e.g., St. John's Wort and traditional Chinese medicine), used from first IP administration until the ESV (including washout between periods) will be considered concomitant medication.

Subjects will only be allowed to use the following concomitant medication, if needed, from first IP administration until the ESV (including washout between periods):

- Paracetamol (up to 2 g/day)
- Topical dermatological products, including corticosteroid products
- Hormonal contraceptives
- HRT

If a subject's health condition necessitates the use of any medication other than the permitted medications during the study, the investigator and medical monitor, or designee(s), will discuss the case and determine if the subject should be withdrawn from the study and/or excluded from analysis sets, depending on if, and how, the medication(s) used influence(s) the study outcome. The nonpermitted concomitant medication will be recorded as a protocol deviation.

All concomitant treatment (medication and nonmedication therapy) will be documented.

Duration of Dosing:

Two single periods separated by a washout of at least 10 days between IP administrations in each period

Dosing Discontinuation Criteria:

A subject must discontinue study dosing for any of the following reasons:

- Subject requests to stop dosing
- Any clinical adverse event (AE), laboratory abnormality or intercurrent illness, in the opinion of the investigator, indicates continued dosing is not in the best interest of the subject
- Hepatic function parameters: ALT or AST $> 3 \times$ ULN and/or TBL $> 2 \times$ ULN
- Cardiac repolarization dysfunction: QTcF > 500 msec and/or if QTcF change from baseline > 60 msec at repeat measurements

Statistical Methods:

Sample Size Justification:

A total of 24 subjects (12 subjects per dose group) will be enrolled. Subjects who discontinue early from the study may be replaced at the discretion of the sponsor.

Based on data from Study 178-CL-091, a Chinese phase 1 study, the intrasubject coefficient of variation (CV) for pharmacokinetic parameters AUC_{inf} , AUC_{last} and C_{max} of the 50 mg mirabegron dose are estimated to be between 33% and 60%. Assuming the underlying variability is similar to 60% and an observed ratio between fasted and fed conditions of 100%, the 90% CI will lie within (60, 167) with $> 80\%$ probability.

Efficacy:

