9.2.1 Safety Analysis Set

The safety analysis set (SAF) consists of all subjects who receive at least 1 dose of IP.

The SAF will be used for all summaries and analyses of the safety data.

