9.2.2 Pharmacokinetic Analysis Set

The pharmacokinetic analysis set (PKAS) consists of all subjects who receive at least 1 dose of IP for which concentration data are available to facilitate derivation of at least 1 primary pharmacokinetic parameter. Inclusion of subjects in the PKAS with missing data or major protocol deviations will be considered by the pharmacokineticist on a case-by-case basis.

The PKAS will be used for all summaries and analyses of the pharmacokinetic data.

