10.3 Major Protocol Deviations

A protocol deviation is generally an unplanned excursion from the protocol that is not implemented or intended as a systematic change. All deviations from the protocol are to be recorded. A protocol waiver is a documented prospective approval of a request from an investigator to deviate from the protocol. Protocol waivers are strictly prohibited.

The investigator is responsible for ensuring the study is conducted in accordance with the procedures and evaluations described in this protocol and must protect the rights, safety and well-being of subjects. The investigator should not implement any deviation from, or changes of, the protocol, unless it is necessary to eliminate an immediate hazard to subjects.

A major protocol deviation is one that may potentially impact the completeness, accuracy or reliability of data contributing to the primary endpoint or affect the rights, safety or well-being of a subject. Major protocol deviations will have additional reporting requirements.

When a major deviation from the protocol is identified for an individual subject, the investigator or designee must ensure the sponsor is notified. The sponsor will follow up with the investigator, as applicable, to assess the deviation and the possible impact to the safety and/or pharmacokinetic parameters of the subject to determine subject continuation in the study.

The major protocol deviation criteria that will be summarized at the end of the study are as follows:

PD1 - Entered into the study even though the subject did not satisfy entry criteria

PD2 - Developed withdrawal criteria during the study and was not withdrawn

PD3 - Received incorrect dose

PD4 - Received excluded concomitant treatment

The investigator will also assure that deviations meeting IRB/IEC and appropriate regulatory authorities' criteria are documented and communicated appropriately. All documentation and communications to the IRB/IEC and appropriate regulatory authorities will be provided to the sponsor and maintained within the trial master file.

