## 4 ANALYSIS SETS

In accordance with International Conference on Harmonization (ICH) recommendations in guidelines E3 and E9, the following analysis sets will be used for the analyses.

The determination of whether subjects are included or excluded from the safety analysis set will be made prior to database hard-lock.

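### Does the rule on non-permitted medication let a dosed subject be dropped from the safety analysis set, or leave membership of the pharmacokinetic analysis set (PKAS) undecided?

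*Protocol*

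**What the plan says.** Protocol 6.5.2 allows four classes of concomitant medication from first dose to the end-of-study visit. If a subject's health requires anything else, the investigator and medical monitor, or their designees, discuss the case and "determine if the subject should be withdrawn from the study and/or excluded from analysis sets". The test is "depending on if, and how, the medication(s) used influence(s) the study outcome". Section 6.5.2 adds that "The nonpermitted concomitant medication will be recorded as a protocol deviation", with a pointer to Section 9.9. The synopsis (1.1) carries the same rule without the pointer.

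The analysis sets are defined elsewhere. Protocol 9.2.1 and SAP 4.1 agree: "The safety analysis set (SAF) consists of all subjects who receive at least 1 dose of IP". Both use the SAF for all safety summaries. For the PKAS, Protocol 9.2.2 and SAP 4.2 require concentration data sufficient to derive at least one primary parameter, and add: "Inclusion of subjects in the PKAS with missing data or major protocol deviations will be considered by the pharmacokineticist on a case-by-case basis".

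The only commitment on when membership is settled is in SAP 4: "The determination of whether subjects are included or excluded from the safety analysis set will be made prior to database hard-lock". Protocol 10.3 lists "PD4 - Received excluded concomitant treatment" among the major deviations. Protocol 12.6, the list of excluded medications, is marked not applicable.

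**The concern.** Three things look wrong on a first reading.

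- **The safety set.** The 6.5.2 rule applies to medication used after the first dose, so the subject already belongs to the SAF. An unqualified plural takes in the SAF, whose definition allows no exception. The sentence in SAP 4 on inclusion in or exclusion from the SAF could be read as supporting discretion. A subject who needed treatment is one the safety tables should not lose.
- **The decider.** Section 6.5.2 gives the exclusion decision to the investigator and medical monitor. Sections 9.2.2 and SAP 4.2 have the pharmacokineticist consider subjects with major deviations. One subject can fall under both, and no text says how one decision passes to the other. Protocol 10.3 does not settle it, because the sponsor follow-up described there concerns continuation in the study.
- **The timing.** The hard-lock commitment names the set with nothing discretionary in it. The PKAS, which is discretionary and feeds the primary fed/fasted analysis, has no stated cut-off. The study is open-label, so in principle an exclusion could be decided with the results in view.

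**Working it through.** **Which set the phrase can mean.** Set the provisions side by side.

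| Place | SAF | PKAS |
|---|---|---|
| Definition (Protocol 9.2, SAP 4.1 and 4.2) | All dosed subjects, no exception | Data-dependent, with case-by-case review |
| Who judges membership | Nobody; dosing is a fact | Pharmacokineticist |
| Timing stated (SAP 4) | Before hard-lock | None |
| Fit with the 6.5.2 test (influence on study outcome) | Poor | Good |

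The specific definition governs a general phrase in a concomitant-medication section. The SAP, which directs the analysis, contains no medication-based exclusion from the SAF. The SAP 4 sentence sets a time. Checking whether each subject was dosed also sorts subjects in and out, so the sentence implies no discretion.

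**Whether a non-permitted medicine is a major deviation.** Section 6.5.2 points to 9.9, which points to 10.3, where PD4 covers excluded treatment. Because 6.5.2 works by a list of what is allowed, a list of excluded drugs is unnecessary, and the entry in 12.6 creates no real doubt. The link to PD4 is an inference, but a safe one.

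**The plan's own precision figure (Protocol 9.1, SAP 3).** Inputs: 12 subjects per dose group, assumed here to be 6 per sequence as in the design table; intrasubject CV 60%; observed ratio 100%; limits 60% and 167%.

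- s_w = √ln(1 + CV²) = √ln(1.36) = 0.5545
- Half-width on the log scale = t(0.95, df) × s × √[0.5(1/n₁ + 1/n₂)], with df = n₁ + n₂ − 2
- Lower limit: −ln 0.60 = 0.5108, marginally the tighter of the two
- Probability that the half-width is at most 0.5108 = P(χ²_df ≤ df × [0.5108/(t × s_w × √(0.5(1/n₁ + 1/n₂)))]²)
- For 6+6: df = 10, t = 1.8125, root = 0.4082, half-width at s = s_w is 0.4103; P(χ²₁₀ ≤ 10 × 1.245²) = 88.5%

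The plan states more than 80%, so its figure reproduces.

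**Losing one PKAS subject without replacement (6+5).** df = 9, t = 1.8331, root = 0.4282.

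| CV | s_w | Half-width 6+6 | Half-width 6+5 | 90% CI around 100%, 6+6 | 90% CI around 100%, 6+5 |
|---|---|---|---|---|---|
| 33% | 0.3215 | 0.2379 | 0.2524 | 78.8–126.9% | 77.7–128.7% |
| 60% | 0.5545 | 0.4103 | 0.4352 | 66.3–150.7% | 64.7–154.5% |

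The ratio of half-widths is (1.8331 × 0.4282)/(1.8125 × 0.4082) = 1.061 at either CV, a widening of 6.1%. The precision probability at CV 60% becomes 80.8% with 6+5 and 72.2% with 5+5.

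**Losing one SAF subject, if the literal reading were followed.** With 12 dosed subjects per dose-by-food cell, 1/12 (8.3%) becomes 0/11 (0%), or 2/12 (16.7%) becomes 1/11 (9.1%).

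**What these figures measure.** The PK figures give the cost of losing any subject for any reason, and clearer wording would not alter them. The safety figures arise only under a reading that the SAF definition rules out.

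**The case for a change.** The strongest case for a change is that the repair is cheap and the group is small. Two unreplaced PKAS exclusions in one dose group, one from each sequence, would take the plan's precision from 88.5% to 72.2%, below the 80% it states. Replacement is at the sponsor's discretion and is described for subjects who discontinue early. In an open-label study, fixing discretionary exclusions before the fed/fasted ANOVA is ordinary good practice, and the one deadline given is attached to the set that least needs it.

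Part of this stands. The documents state no hand-off and no PKAS cut-off, and a sentence supplying both would do no harm. But the roles read naturally as sequential: the clinical discussion informs, and the pharmacokineticist is the role both documents attach to PKAS membership. PKAS membership also depends on concentration data, so it cannot be fixed from dosing records as the SAF can, which makes its absence from the SAP 4 sentence understandable. A cut-off before the ANOVA would protect only partly, since individual concentrations under each condition can be seen before any model is fitted. The loss of precision would be the same under a perfectly drafted rule.

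**Conclusion.** No change to the plan follows. The reference to analysis sets in Protocol 1.1 and 6.5.2 is loose, but the SAF definition leaves no room to exclude a dosed subject, so the phrase can sensibly mean only the PKAS. For the PKAS, the missing hand-off and cut-off are details that the pharmacokineticist and statistician would ordinarily settle in practice.

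No bias in the primary ratios is shown, and no result is shown to depend on the wording. The 6.1% widening per lost subject assumes 6 per sequence, no replacement and the crossover formula above; it is not a consequence of this text. Adverse events (Protocol 9.5.1), major deviations (SAP 6.2.2), concomitant treatments (SAP 6.2.4) and PK parameters (SAP 6.5.2) are all listed, which leaves a record against which an exclusion can be examined.

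The conclusion assumes that analysts follow the set definitions in the SAP and that the pharmacokineticist makes the final PKAS decision. It would need another look if a dosed subject were in fact left out of the safety tables, or if a PKAS exclusion were made after the food-effect results were known.

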6.6 Dose Modification

Not applicable.

6.7 Criteria for Continuation of Dosing

Not applicable.

7 STUDY PROCEDURES AND ASSESSMENTS

7.1 Efficacy Assessments

Not applicable.

7.2 Safety Assessments

7.2.1 Adverse Events

See [Section 7.3 Adverse Events and Other Safety Aspects] for information regarding AE collection and data handling.

7.2.2 Laboratory Assessments

Clinical laboratory tests will be performed at a local laboratory.

Blood samples will be collected via a peripherally placed intravenous cannula or by direct venipuncture in a suitable forearm vein.

Blood samples for hematology and biochemistry and urine samples for urinalysis will be collected as indicated in the Schedule of Assessments [Table 1]. The clinical laboratory tests to be performed in the study are listed in [Appendix 12.7 Laboratory Assessments].

A blood sample will be collected for serology tests (HAV antibodies [IgM], HBc antibodies, HBsAg, HCV antibodies, HIV and syphilis) at screening only.

Drugs of abuse and alcohol tests will be performed according to the clinical site's preferred method. Drugs of abuse and alcohol tests will be performed as indicated in the Schedule of Assessments [Table 1].

Serum pregnancy tests (female subjects only) will be performed according to the clinical site's preferred method. Serum pregnancy tests will be performed as indicated in the Schedule of Assessments [Table 1].

A blood sample will be collected for follicle-stimulating hormone (FSH) tests (postmenopausal female subjects only) as indicated in the Schedule of Assessments [Table 1].

If any of the clinical laboratory tests results be outside the normal range at any scheduled time point during the study, the investigator may decide to repeat the test(s) on new samples. The clinical relevance of the abnormal results will be documented. Clinically relevant

changes will be recorded as AEs (see [Section 7.3 Adverse Events and Other Safety Aspects]).

7.2.3 Vital Signs

Blood pressure (SBP and DBP), body temperature and pulse measurements will be taken as indicated in the Schedule of Assessments [Table 1]. Measurements will be taken after the subject has been resting in the supine position for at least 5 minutes. Blood pressure and pulse measurements will be taken in triplicate with approximately 2-minute intervals at screening and on day -1 of each period (the mean will be used). At all other time points and for body temperature, single measurements will be taken.

7.2.4 Physical Examination

Physical examination will be performed as indicated in the Schedule of Assessments [Table 1] and whenever there is a medical indication.

The investigator should perform physical examinations in accordance with routine procedures. Any abnormal finding observed at screening must be assessed and documented as not clinically significant if a subject is to be enrolled in the study. After IP administration, new clinically significant findings or a worsening of an ongoing clinically significant abnormal condition will be recorded as an AE (see [Section 7.3 Adverse Events and Other Safety Aspects]).

7.2.5 Electrocardiogram

7.2.5.1 Routine 12-lead Electrocardiogram

Routine (12-lead) ECGs will be taken as indicated in the Schedule of Assessments [Table 1]. Routine 12-lead ECGs will be taken after the subject has been resting in the supine position for at least 5 minutes. Routine 12-lead ECGs will be taken in triplicate at screening and on day -1 of each period with approximately 1-minute intervals and all 3 ECGs will be completed within 5 minutes. At all other time points, single measurements will be taken.

The investigator will review, sign and date the ECG after recording to ensure subject safety. The time of the ECG, the interval measurements, as well as an overall conclusion, will be documented. This overall conclusion will be recorded as normal, abnormal not clinically significant, or abnormal clinically significant. If the overall conclusion is abnormal, the details must be recorded.

Per time point, the ECG will be stored electronically and reviewed in a timely manner by the investigator. The electronic data file with all generated ECG variables and electronic files with the digitized tracings will be transferred to the sponsor at the end of the study.

7.2.6 Order of Assessments

When time points for procedures overlap, blood sampling for pharmacokinetics will be collected at the nominal time point. Blood and urine sampling for clinical laboratory tests, routine 12-lead ECG and vital signs are to be collected before or after the nominal blood

sampling for pharmacokinetics. Vital signs are recommended to be collected before venipuncture or, if necessary, after venipuncture from the opposite arm.

The allowed collection windows for procedures are shown in [Table 5].

Table 5 Order of Assessments

Assessment	Time Point	Window
Blood Sampling for Pharmacokinetics	Predose	-90 to 0 minutes
	0 to < 4 hours	± 2 minutes
	4 to < 12 hours	± 5 minutes
	12 to < 48 hours	± 15 minutes
	48 hours and thereafter	± 30 minutes
Vital Signs	Predose	-60 to 0 minutes
	0 to < 12 hours	± 15 minutes
	> 12 hours	± 30 minutes

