1.3 Schedule of Assessments

Table 1 Schedule of Assessments

Assessments Day(s)	Screening Period		Periods 1/2 ¹			ESV	Withdrawal
	-21 to -2	-1	1	2 to 4	5	12±2	
Residential Period		X	X	X	X		
Ambulant Visits	X					X	
Informed Consent	X						
Chest X-ray		X ²					
Inclusion and Exclusion Criteria	X	X ²					
Medical History	X	X ²					
Body Weight and Height	X	X ³					
Demographics	X						
Drugs of Abuse and Alcohol Tests	X	X					
Randomization ⁴		X ²					
IP Administration ⁵			X				
Physical Examination	X	X ²	X		X	X	X
Vital Signs (Blood Pressure, Body Temperature and Pulse) ⁶	X	X	predose†, 2, 8, 24, 48, 72 and 96 hours postdose			X	X
Clinical Laboratory Tests (Serology, Hematology, Biochemistry and Urinalysis) ⁷	X	X†			X	X	X
12-lead ECG ⁸	X	X†				X	X
Blood Sampling for Mirabegron Pharmacokinetics			predose, 0.5, 1, 2, 3, 4, 5, 6, 7, 8, 12, 16, 24, 36, 48, 72 and 96 hour(s) postdose				
Serum Pregnancy Test (Female Subjects Only) ⁹	X	X					
FSH Test (Postmenopausal Female Subjects Only)	X						
Adverse Event Assessment				X			
Previous/Concomitant Treatment (Medication and Nonmedication Therapy)				X			

Footnotes appear on the next page

ECG: electrocardiogram; ESV: end-of-study visit; FSH: follicle-stimulating hormone; IP: investigational product; X: to be conducted

† Baseline

1. Periods will be separated by a washout of at least 10 days between IP administrations in each period. There is no washout after period 2.
2. Period 1 only.
3. Body weight only.
4. Subjects will be randomized to 1 of 4 sequences.
5. *Fasted Conditions:* Following an overnight fast of at least 10 hours, subjects will receive a single dose of 25 or 50 mg mirabegron with 240 mL water. Subjects are to remain semirecumbent and avoid lying on either the left or right side for 4 hours postdose. No food or beverage will be allowed for at least 4 hours postdose. Water can be ingested as desired except for 1 hour predose and 1 hour postdose.

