6 INVESTIGATIONAL PRODUCT(S)

6.1 Investigational Product(s) Administered

Table 4 Investigational Product(s)

Name	BETMIGA® (Mirabegron)
Use	Test product
Dosage Formulation	Sustained-release tablet
Physical Description	25 mg: oval, brown, film-coated tablet 50 mg: oval, yellow, film-coated tablet
Dose Strength	25 and 50 mg
Packaging and Labeling	10 tablets per carton
Route of Administration	Oral
Administration Instruction	
Mirabegron will be administered as single oral doses under fed or fasted conditions on day 1 of each period.
 
Fasted Conditions: Following an overnight fast of at least 10 hours, subjects will receive a single dose of 25 or 50 mg mirabegron with 240 mL water. Subjects are to remain semirecumbent and avoid lying on either the left or right side for 4 hours postdose. No food or beverage will be allowed for at least 4 hours postdose. Water can be ingested as desired except for 1 hour predose and 1 hour postdose.
 
Fed Conditions: Following an overnight fast of at least 10 hours, subjects will start a low-fat breakfast. Subjects should eat the breakfast in 30 minutes or less. Subjects will receive a single dose of 25 or 50 mg mirabegron with 240 mL water 30 minutes after the start of the breakfast. Subjects are to remain semirecumbent and avoid lying on either the left or right side for 4 hours postdose. No food or beverage will be allowed for at least 4 hours postdose. Water can be ingested as desired except for 1 hour predose and 1 hour postdose. Except for the day 1 breakfast in each period, subjects will receive standardized meals scheduled at the same time during the stay at the clinical unit. The low-fat meal (total calories approximately 450 kcal, with approximately 70 kcal from fat) is cereal, low fat milk, wheat bread, ham and ketchup.

IMP or Non-IMP	IMP
Sourcing	Provided centrally by sponsor

IMP: investigational medicinal product

Refer to the product label and package insert [Betmiga Package Insert, Aug 2019] for detailed information regarding handling and storage of the IP.

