9.5.3 Vital Signs

Descriptive statistics will be used to summarize vital sign results and changes from baseline for subjects by fed and fasted conditions and time point for each dose group.

Vital signs data will be listed.

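### Does the predose vital-sign window, which is not tied to the breakfast, make the fed and fasted baselines non-comparable?

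*Protocol*

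**What the plan says.** Protocol 7.2.6, Table 5, gives one predose window for vital signs, "60 to 0 minutes" before the dose, for both food conditions. The text above the table orders vital signs only against blood sampling: "Vital signs are recommended to be collected before venipuncture or, if necessary, after venipuncture from the opposite arm". It does not mention breakfast.

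Table 1 (Protocol 1.3) schedules vital signs at "predose†, 2, 8, 24, 48, 72 and 96 hours postdose", and the dagger marks the predose reading as baseline. SAP 6.4.3 takes the last available value before dosing within each period as baseline.

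For the fed condition, Table 4 (Protocol 6.1) says "Subjects should eat the breakfast in 30 minutes or less" and "Subjects will receive a single dose of 25 or 50 mg mirabegron with 240 mL water 30 minutes after the start of the breakfast".

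On the measurement itself, Protocol 7.2.3 says "Measurements will be taken after the subject has been resting in the supine position for at least 5 minutes". Blood pressure and pulse are taken in triplicate at screening and on day -1 of each period; beyond that, "At all other time points and for body temperature, single measurements will be taken".

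The use of the data is set in Protocol 9.5.3: descriptive statistics will "summarize vital sign results and changes from baseline for subjects by fed and fasted conditions and time point for each dose group". SAP 6.4.3 plans the same summary, and both documents also list the data.

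**The concern.** The study compares fed with fasted dosing, so anything that differs systematically between the two conditions deserves a check. In the fed period the permitted predose window runs across the start of breakfast; in the fasted period there is no meal. If some fed baselines came after the meal and others before it, the fed changes from baseline would rest on a mixture and the fasted changes would not. Such a shift would follow food condition in both sequences, so the crossover would not cancel it.

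The day -1 triplicate does not prevent this, because the later single predose reading replaces it as the last value before dosing. The general baseline definition in Protocol section 9 (last value before the first dose) would not prevent it either: the period 1 reading is fed in one sequence and fasted in the other. Quality tolerance limit 2 (Protocol 12.2.4) tracks meal and dosing times, not when vital signs are taken relative to the meal.

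At stake would be the comparison of vital-sign changes between conditions. Vital signs are a secondary endpoint, and increased heart rate and increased blood pressure are adverse events of special interest (Protocol 7.3.6).

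**Working it through.** The plan states no figure to reproduce. The check sets its clock times side by side, with the dose at 0.

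**1. Nominal overlap.** The vital-sign window is [-60, 0] minutes (Table 5). Breakfast starts at 0 - 30 = -30 (Table 4). In the fed period 30 of the 60 permitted minutes follow the start of the meal; in the fasted period none do.

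**2. Minutes in which a post-meal reading is possible.** A reading needs at least 5 minutes supine (Protocol 7.2.3), which makes a reading during the meal unlikely. The realistic case is a breakfast finished early, then the rest, then the reading. With eating time m, the room left is max(0, 30 - m - 5) = max(0, 25 - m). The protocol gives only the upper limit of 30 minutes for m; the lower values are assumptions. The share is the post-meal minutes divided by those minutes plus the 30 minutes before breakfast.

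| Eating time m (min) | Post-meal minutes | Share of usable window |
|---|---|---|
| 10 | 15 | 15/45 = 33% |
| 15 | 10 | 10/40 = 25% |
| 20 | 5 | 5/35 = 14% |
| 25 or more | 0 | 0% |

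These are permitted minutes, not expected readings. A post-meal reading also requires that the subject lies down straight after eating and is measured just before the dose.

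**3. Effect on the summary.** Let k of the 12 fed baselines in a dose group follow the meal, and let the meal shift the reading by d. The mean fed change then moves by -(k/12)d at each of the six postdose times: 0 at k = 0, -0.25d at k = 3, -0.5d at k = 6 and -d at k = 12. The documents give neither k nor d, so no size can be derived.

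**4. Would a baseline fixed before breakfast settle it?** Let e be the part of the meal's effect still present at a given postdose time. The mean fed change is then (drug effect) + e - (k/12)d.
- With all baselines before the meal (k = 0) it equals drug effect + e. That is the drug effect alone only if e = 0.
- With all baselines after the meal (k = 12) it equals drug effect + e - d. That is the drug effect alone only if e = d.

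At 2 hours, the first postdose reading, the documents support neither e = 0 nor e = d. Which baseline is right depends on whether the fed change is meant to describe the drug alone or the drug plus the meal. The plan does not say, and it tests neither.

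**5. What depends on this baseline.** Vital signs are summarized without a test. The named limits for stopping dosing in Protocol 8.1 are hepatic values and QTcF, not vital-sign change. The primary model (Protocol 9.6.3, SAP 6.5.3) uses AUCinf, AUClast and Cmax only.

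**The case for a change.** The strongest case for acting is that the sponsor already accepts the principle. Quality tolerance limit 2 exists because meal and dosing times outside their window can affect the evaluation of the food effect, and fixing the baseline against the meal applies the same reasoning. The remedy would be one line in Table 5 with no added measurement. A post-meal fed baseline would comply with the protocol, so no deviation would be raised, and a mixture of baselines serves neither purpose set out in step 4 cleanly.

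Part of this stands. No section orders the reading against breakfast, and a uniform rule would be tidier. At the later times, from 24 hours on, it is reasonable to assume that nothing of the breakfast effect remains; a pre-meal baseline would then be the cleaner one.

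What does not stand is the step from an open window to a faulty comparison. The documents permit a post-meal reading but do not make it likely. The predose pharmacokinetic sample may be drawn from 90 minutes before dosing, and vital signs are recommended before venipuncture. Where that sample is drawn before breakfast, the recommendation favours a pre-meal reading, although it does not require one. Results are also summarized alongside changes, and each subject has a triplicate day -1 reading of blood pressure and pulse in each period. A reader can therefore check the predose values against a reference that the dosing-day breakfast cannot affect, within the limits of 12 subjects per dose group.

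**Conclusion.** The concern does not hold as an error. The clock times are right and the order is unspecified, but the sections do not contradict each other, and following them as written gives no demonstrably wrong result. A post-meal fed baseline is possible in 0 to 15 permitted minutes, for assumed eating times of 30 down to 10 minutes. The resulting shift in the mean fed change lies between 0 and -d, where d is not in the documents and may be zero. It would touch only a descriptive secondary summary that is reported together with the raw values.

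Fixing the baseline before breakfast would make it uniform, but any meal effect at 2 hours would remain wholly in the fed change. Whether to do so is a judgement about what that change should describe. The conclusion rests on two points: the summary stays descriptive, and no dosing rule or primary analysis draws on the vital-sign baseline. Both are what the current documents say.
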